Hence, we propose to evaluate the overall hypothesis that intestinal chemosensitivity related to increased epithelial permeability and GLP-1 explains symptom severity in patients with functional dyspepsia and in patients with DM and dyspepsia. 24 healthy subjects, 40 patients with DM and GI symptoms, and 40 patients with functional dyspepsia will undergo assessment of intestinal chemosensitivity during duodenal nutrient perfusion, gastric emptying (by scintigraphy), cardiovascular and GI vagal functions (plasma pancreatic polypeptide response to sham feeding and a comprehensive autonomic reflex screen), in vivo assessment of small intestinal permeability (urinary lactulose:mannitol ratio), and upper endoscopy with assessment of epithelial tight junction proteins and permeability on small bowel biopsies. During the nutrient infusion, subjects in each group (ie, healthy subjects, functional dyspepsia and DM) will be randomized to lipid infusion and placebo or lipid infusion {66.7 mL Microlipid (0.5 gm/mL diluted in water to 222 mL)} and exendin 9-39 in the ratio of 1:1. Hormonal responses (i.e., GLP-1, CCK, GIP, glucagon, PYY, C-peptide, and insulin) and plasma glucose will also be evaluated during enteral nutrient infusion. GI symptoms during each perturbation (meal, nutrient infusion) will be evaluated by validated questionnaires. Blood will be collected for DNA-based genetic analyses, initially to assess the relationship of GI sensorimotor dysfunctions and symptoms with SNPs affecting CCK and GLP-1 receptors. The analysis will assess for disturbances in these parameters in functional and DM dyspepsia, investigate associations between symptoms during enteral infusion and hormonal-epithelial functions, and evaluate relationships between daily symptoms and results of testing.

Table of Contents

ABSTRACT.....	1
1 SPECIFIC AIMS	3
2 BACKGROUND AND SIGNIFICANCE.....	5
3 RESEARCH DESIGN AND METHODS.....	7
3.1 Study Design.....	7
3.2 Study Subjects.....	7
3.3 Details of Study Assessments	8
3.4 Gene and Epigenetic Studies	15
3.5 Data Analysis	16
3.6 Potential Pitfalls.....	17
4 HUMAN SUBJECTS	17
5 SAFETY AND ADVERSE EVENTS	19
5.1 Definitions.....	19
5.2 Recording of Adverse Events	21
5.3 Reporting of Serious Adverse Events and Unanticipated Problems.....	22
5.3.1 Sponsor-Investigator reporting: notifying the Mayo IRB.....	22
5.3.2 Sponsor-Investigator reporting: Notifying the FDA.....	22
5.4 Stopping Rules	23
5.5. Medical Monitoring	23
APPENDIX.....	23

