- 2) **Intestinal chemosensitivity will be A) associated with higher plasma CCK and GLP-1 concentrations B) reduced by the GLP-1 antagonist exendin 9-39 and C) inversely associated with impaired abdominal vagal function.** This hypothesis will be evaluated by comparing intestinal chemosensitivity (a) with plasma CCK and GLP-1 concentrations (b) with and without exendin 9-39 and (c) in patients with and without and GI vagal dysfunction as assessed by the plasma pancreatic polypeptide response to sham feeding.
- 3) **A) Patients with DM and GI symptoms have abnormal epithelial tight junction proteins which predispose to increased epithelial permeability and increased small bowel permeability and B) These structural and functional markers of epithelial permeability are associated with intestinal chemosensitivity.** Intestinal permeability will be measured in vivo by two sugar urine excretion after oral ingestion. Biopsies from the distal second or third portion of the duodenum will be obtained endoscopically, to measure various markers of epithelial structure and function.

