Vagal dysfunction has been implicated as a mechanism for GI sensorimotor dysfunctions in DM¹⁴. The plasma pancreatic polypeptide (PP) response to sham feeding evaluates GI vagal function¹⁵. In clinical practice, assessment of cardiovascular vagal functions is used as a surrogate measure of GI vagal dysfunction. Only 1 study evaluated the relationship between cardiovascular and GI vagal dysfunction (i.e., gastric acid secretion, PP response to sham feeding) and observed a modest correlation¹⁵. The utility of the sham feeding response and cardiovascular measures to predict upper GI sensorimotor dysfunctions is unknown and will be evaluated in this study.

Small intestinal epithelial permeability and mucosal inflammation

A recent study suggests that patients with functional dyspepsia have low-grade mucosal inflammation, abnormalities of cell-to-cell adhesion proteins which predispose to increased epithelial permeability, and a leaky epithelial barrier¹⁶. Type 1 DM is associated with increased small intestinal permeability even in subjects who do not have celiac disease^{17,18}. Moreover, a comparison of 339 type 1 DM patients and 89 first degree relatives observed higher serum zonulin levels in type 1 DM patients than controls or relatives; patients with increased zonulin had increased epithelial permeability¹⁹. The only study which evaluated small intestinal permeability in type 2 DM used suboptimal techniques and reported normal permeability²⁰. However, a high fat diet induced glucose intolerance, decreased intestinal tight junction proteins, increased epithelial permeability, and plasma concentrations of circulating cytokines in OLETF mice, which is a

Small intestinal dysmotility, more frequently characterized by reduced than by increased motility²⁷, may also contribute to gastric stasis in DM. We recently observed increased sensitivity during duodenal carbohydrate and separately lipid perfusion in approximately 50% of patients with functional dyspepsia (Figure 1). Moreover, increased sensitivity was associated with higher plasma concentrations of GLP-1 during lipid infusion and more severe dyspeptic symptoms during daily life (unpublished data). Previous

spontaneous CCK-1 receptor knockout mouse and an animal model of obesity³². Given the similarities between this mouse model and type 2-DM in humans, it is conceivable that epithelial permeability is also increased in type 2 DM.

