3.2 Study Subjects

We plan to accrue up to 115 subjects to ensure that 104 subjects complete the study in its entirety. 40 patients with DM and GI symptoms and 40 patients with functional dyspepsia will be recruited from the clinical practice; 24 healthy subjects will be recruited by public advertisement. To reduce the possibility of demographic differences between controls and patients, we will "frequency match" on age and gender by recruiting 5 controls after each set of 5 patients is studied. Doing so will provide similar age and gender distribution in each type. We will also attempt to recruit an even number of subjects with type 1 and 2 DM.

Inclusion criteria for controls

1. Healthy male or non-pregnant, non-breastfeeding female volunteers;
2. 18-70 years old;
3. Able to provide written informed consent before participating in the study;
4. Able to communicate adequately with the investigator and to comply with the requirements for the entire study

Additional inclusion criteria for patients

1. Symptoms of dyspepsia (i.e., early satiety, postprandial discomfort, nausea, vomiting, regurgitation)

2. Patients in the DM group will also require Type 1 or 2 DM of \geq 3 years duration; in patients with type 2 DM, the dyspepsia symptoms should have begun or worsened after DM was diagnosed

Exclusion criteria – for patients and controls

1. Major abdominal surgery (i.e., appendectomy, cholecystectomy, tubal ligation, hysterectomy, and limited colonic resection are permissible)
2. Clinical evidence (including physical exam and EKG) of significant cardiovascular, respiratory, renal, hepatic, gastrointestinal, hematological, neurological, psychiatric or other disease that may interfere with the objectives of the study and/or pose safety concerns
3. Opiates, alpha adrenergic agonists, metoclopramide, and high doses of anticholinergic agents (eg, amitriptyline greater than 50 mg daily). If medically safe, these drugs may be discontinued for four half lives prior to study assessments
4. Treatment with GLP-1 agonists and amlodipine which cause vagal blockade and may affect central processing of pain
5. Use of tobacco products within the past 1 week or NSAIDs or aspirin within the past week (since they all may affect intestinal permeability)
6. Bleeding or clotting disorders or medications that increase risk of bleeding from mucosal biopsies
7. Positive tissue transglutaminase antibodies (TTG),

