3.3 Details of Study Assessments

In patients with DM, fingerstick bedside reflectance meter blood glucose concentrations will be assessed during enteral infusion and gastric emptying studies at time 0, every 30 minutes for 2h, then at 120 and 180 minutes. For patients with type 1 and type 2 DM who are treated with insulin, insulin will be given according to the patient's sliding scale. For type 2 DM patients who are not on insulin, no insulin will be given.

i) Screening items include questionnaires (for overall functional GI symptoms [Rome III criteria], severity of dyspepsia [Nepean severity index], gastroparesis cardinal symptom index [GCSI], anxiety and depression [HAD], and autonomic symptoms), blood tests (CBC, glycosylated hemoglobin, fasting glucose, sodium, potassium, bicarbonate, calcium, chloride, phosphorous, AST, total bilirubin, alkaline phosphatase, creatinine, high sensitive C-reactive protein, tissue transglutaminase antibodies, and lipase), and EKG (to be reviewed by study physician). Some patients with diabetes mellitus have low serum lipase. Patients with serum lipase < lower limit of normal (i.e., < 10 IU/ml) will not be eligible to participate in the study.

Study procedures will be conducted over 3 days. Items (ii), (iii), (iv), and (v) below will be performed on the same day preferably before other study procedures. A tentative schedule is as follows: (ii) between 8 and 8.45 am, (iii) between 8.45 am and 11 am, (iv) can start while (iii) is in progress and (v) between 12.30 pm and 3 pm.

ii) Plasma pancreatic polypeptide (PP) response to sham feeding. Pancreatic polypeptide (PP) is secreted by the pancreas in response to hypoglycemia, ingestion of food or sham feeding secondary to vagal nerve stimulation. Vagal nerve injury blocks secretion. This assessment will be performed in the Charlton 7 CRU. Subjects will be fasting with NPO for 8 hours prior to this test. They must abstain from coffee or for 12 hours and stop all cholinergic agents for 48 hours before the test. During the sham feeding test, food is chewed and spit out (not swallowed) . After placement of an IV in the hand or forearm vein for blood draws, this hand will be placed in a hotbox heated to 55°C. Blood will be drawn in a lavender-top (EDTA) tube(s) at -5, 0, 5, 10, 15, 20, 25, and 30 minutes for PP. Spin down, keep specimen cold, and send 1.0 mL (0.5 mL minimum) of EDTA plasma frozen in plastic vial.

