3.5 Data Analysis

Chemosensitivity will be measured using a 100mmVAS anchored at each end (left end:No symptoms, right end: Severe symptoms). The distribution of this measure will be checked for its approximation to a gaussian distribution. An analysis to provide preliminary data for a new grant submission will be examined after approximately 15 subjects (5 DM, 10 controls) have completed the studies, but there is no intention of stopping the study based on the preliminary results. We anticipate conducting this analysis in July 2014 or thereafter.

Question	Summary Parameter	Statistical analysis
Sensation (symptoms) during enteral infusion (Aim 1)	VAS score	i) compare VAS scores in response to lipid infusion + exendin vs. lipid infusion + placebo separately for each group using a 2-sample t-test or Wilcoxon rank sum test ii) compare the delta VAS scores (exendin – placebo) to assess the association with subject status (FD,DM, and controls) using an ANOVA model (adjusting for covariates, eg, type of DM) or Kruskal-Wallis test.
Relationship between intestinal chemosensitivity and severity of ongoing upper GI symptoms	Mean symptom score and QoL defined by the Nepean dyspepsia index and GCSI diary	Multiple linear regression with the dependent variable = mean symptom score, and separately the QoL score (possibly after rank transformation). Potential predictor variables = VAS score during enteral lipid + placebo infusion, gastric emptying, age, gender, BMI
Relationship between sensation and plasma hormones during lipid infusion (Aim 2)	Using the VAS score from the enteral infusions and for hormones, the AUC values	Spearman correlations between the VAS score and the AUC values for the various hormones, overall and separately by group (FD,DM, controls)
Small intestinal tight junction proteins,	Protein expression, lactulose:mannitol	Assess the associations between permeability and protein expression, vs. the VAS score, based on Spearman

permeability, intestinal chemosensitivity	ratio, VAS score	correlations.
---	------------------	---------------

The sample size estimate is based on our previous study which evaluated intestinal chemosensitivity in functional dyspepsia in which the proportions with severe symptoms were assessed. [In the current proposal, symptoms during lipid infusion will be evaluated on a continuous VAS scale, likely providing the ability to detect smaller effect sizes]. The effect of lipid plus

Group	Proportions (%) with severe symptoms			

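### The drug hold before the sham-feeding test names only cholinergic agents, so a permitted anticholinergic could lower the pancreatic polypeptide response and be read as vagal dysfunction

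*Combined protocol and SAP*

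**What the plan says.** Section 3.3 ii describes the PP response to sham feeding as vagally mediated and blocked by vagal injury. Among the preparations for the test, participants must "stop all cholinergic agents for 48 hours before the test".

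Section 3.2, exclusion 3, lists "high doses of anticholinergic agents (eg, amitriptyline greater than 50 mg daily" among the excluded drugs, and adds: "If medically safe, these drugs may be discontinued for four half lives prior to study assessments". The washout is optional and refers to the excluded drugs. A participant below the dose limit is eligible and falls outside it. Exclusion 4 removes other drugs on the stated ground of vagal interference: "Treatment with GLP-1 agonists and amlodipine which cause vagal blockade".

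The PP result has three intended uses:
- Aim 2C (section 1) compares intestinal chemosensitivity "in patients with and without and GI vagal dysfunction as assessed by the plasma pancreatic polypeptide response to sham feeding".
- Section 2 says that the "utility of the sham feeding response and cardiovascular measures to predict upper GI sensorimotor dysfunctions is unknown and will be evaluated".
- The abstract lists PP among the tests and states: "The analysis will assess for disturbances in these parameters in functional and DM dyspepsia". A patient–control comparison of PP is inferred from this; it is not spelled out.

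The analysis table in section 3.5 has no row for PP, no cut for an impaired response and no medication covariate. Its one row tagged to Aim 2 concerns hormones measured during the lipid infusion.

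**The concern.** The hold is an operating instruction for the test that stands for GI vagal function. Read literally, it does not reach a drug class that could imitate the abnormality being measured. A patient with an intact vagus who takes a permitted anticholinergic may show a blunted PP response and be counted as having vagal dysfunction.

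In Aim 2C the bias can go either way. The hypothesis is that impaired vagal function goes with lower chemosensitivity. If drug users also report fewer symptoms during the infusion, the drug produces that pattern without any neuropathy. If users report more symptoms, for instance because sicker patients are the ones treated, a true association is hidden. In a patient–control comparison of PP, use concentrated in patients pushes toward a finding of impairment. If exposure is not recorded at the test, a drug effect may not be separable from neuropathy afterwards.

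**Working it through.** **Reading the text.** The hold covers cholinergic agents. The eligibility rule leaves lower-dose anticholinergics in. The washout covers only excluded drugs. No analysis in section 3.5 adjusts for medication. The gap therefore exists on the text alone. The plan gives no figure to reproduce.

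**Assumed inputs, because the documents give none.** Use f = 10–30% of patients. PP lowered by d = 0.25–1.5 SD in users. Infusion VAS shifted by v SD in users. PP standardized to mean 0 and SD 1 off drug.

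**1. Misclassified patients of 40, with an assumed cut at the 5th percentile.**
Extra patients = 40 × f × [Φ(−1.645 + d) − 0.05].

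| d (SD) | Φ(−1.645 + d) | f = 10% | f = 30% |
|---|---|---|---|
| 0.25 | 0.0815 | 0.1 | 0.4 |
| 0.5 | 0.126 | 0.3 | 0.9 |
| 1 | 0.260 | 0.8 | 2.5 |
| 1.5 | 0.442 | 1.6 | 4.7 |

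**2. Aim 2C as a correlation without a cut.** Simulation with 20,000 runs per cell and n = 40 (the 20 functional dyspepsia and 20 DM patients on placebo plus lipid). PP = PP0 − d·D and VAS = ρ·PP0 + √(1 − ρ²)·e + v·D, where D marks a user; Pearson test, two-sided 0.05.

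- False positives (ρ = 0), f from 10% to 30%:
  - v = 0: about 5%.
  - v = −0.5: 5–6% at d = 0.25–0.5, and 6–12% at d = 1–1.5.
  - v = −0.8: 5–7% at d = 0.25–0.5, up to 14% at d = 1, and 22% in the most extreme cell (d = 1.5, f = 30%).
- Power at ρ = 0.4, about 74% with no drug:
  - v = 0: 72–74% at d = 0.25–0.5, and 56–70% at d = 1–1.5.
  - v = +0.5: 56–70% at d = 0.25–0.5, and 22–58% at d = 1–1.5.

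**3. PP in 40 patients versus 24 controls, use in patients only.** Mean shift = f × d, from 0.10 × 0.25 = 0.025 SD to 0.30 × 1.5 = 0.45 SD. Simulated false positives are 5–9% at d = 0.25–0.5 and 6–32% at d = 1–1.5.

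**4. Does adjusting for on-drug status work?** If every user has the same drug effect, adjustment returns false positives to about 5% and power to about 73%. If individual effects vary (uniform from 0 to 2 times the mean, PP and VAS scaled together, f = 30%), adjusted false positives are 7–10% at mean d = 1–1.5 with v = −0.8. Adjusted power is 45–56% at the same d with v = +0.5. At d = 0.5 and v = −0.5, adjusted false positives are about 5%. Adjustment reduces the bias but does not always remove it.

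**5. Is 48 hours long enough?** Fraction left = 2^(−48/half-life). This is 6% at 12 hours, 25% at 24 hours and 40% at 36 hours (half-lives assumed). The 48-hour hold matches the four half-lives of section 3.2 only for half-lives of 12 hours or less.

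**The case against.** A reader might infer that the word is simply a slip for the opposite class, and that swapping it is the correction. The documents do not show this. On the protocol's own account of PP, a cholinergic drug could raise the response and hide vagal dysfunction, so the hold as written makes sense. The phrase could also loosely mean any drug acting on that system. A word seems to be missing from the same sentence, after the mention of coffee, which makes it poor ground for an argument about a lost prefix. A swap would delete a sensible precaution. This objection stands: the hold is incomplete, and it has not been shown to be wrong.

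Allowing lower doses also looks deliberate. Exclusion 3 sets a dose limit, and the last general exclusion lets the investigator exclude for prior therapy. No text says that permitted doses lower PP, and the remark on vagal blockade concerns other drugs. This stands as a limit on how strongly the harm can be put. It does not close the gap, because discretion at entry is neither a hold nor a record at the test.

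Every driver of the magnitude is assumed. Section 1 does not restrict Aim 2C to the placebo arm, and the figures up to 32% belong to a comparison inferred from the abstract. This stands too, and the simulation should carry little weight beyond showing where the problem starts to matter. The missing PP row and cut are separate gaps and are not evidence about the hold.

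**Conclusion.** The point holds in a limited form and is minor, with medium confidence. The text establishes the gap. The harm rests on two things that the documents do not state: that some participants take permitted anticholinergics, and that those doses lower PP.

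If the drop is 0.25–0.5 SD, the effect is small: fewer than one extra misclassified patient of 40 at the assumed cut, and Aim 2C false positives of at most about 7%. Power can still fall to 56% if users also report more infusion symptoms. The misclassification and false-positive harms become material only at a drop of about 1 SD or more, and the high Aim 2C false-positive rates also need a sizeable shift in users' VAS.

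A reader might infer that the trial's main comparison is compromised. It is not: the randomized exendin–placebo comparison and Aims 1 and 3 do not use PP.

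**What to change.** 1. Reword the instruction in section 3.3 ii to name both cholinergic and anticholinergic agents, held when medically safe for the longer of 48 hours or four half-lives.
2. Record on the case report form any such drug on board at the PP test.
3. Adjust Aim 2C, the section 2 prediction analysis and any PP group comparison for on-drug status.
4. Add a sensitivity analysis that excludes on-drug PP results. It is needed because adjustment can leave bias when drug effects differ between patients.

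**Cost.** One edited sentence, one form field, one covariate and one extra analysis. In the 40 versus 24 comparison with use in patients only, adjusting multiplies the standard error by √[(1/(40 − k) + 1/24) / (1/40 + 1/24)] for k users: 1.02, 1.05 and 1.08 at k = 4, 8 and 12, or 2–8%. The exclusion analysis loses patients. By the Fisher approximation, power at r = 0.4 is Φ(0.4236·√(n − 3) − 1.96). This is 73% at n = 40, 68% at n = 36 (10% use) and 56% at n = 28 (30% use), so it is better as a check than as the main analysis.

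The hold has its own downside. The lipid infusion is on the same day as sham feeding, so held patients would have an off-drug VAS, while gastric emptying (study day 2) and the two-week diary may be on drug. That mixes conditions in Aim 1B. If drugs are held, apply the same hold on study day 2 and state the drug status of the diary. Where a hold is unsafe or unwanted, steps 2 to 4 still reduce the bias.

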3.4 Gene and Epigenetic Studies

i) Towards our long-term objective of uncovering associations between SNPs and dyspepsia and gastroparesis, we propose to extract DNA from blood, to be drawn from study participants. Genome-wide analysis will be conducted using Illumina 610 QUAD microarray or comparable approaches. Genotype-phenotype correlations will be examined using these patients and other patients in ongoing studies.

ii) Epigenetic studies. The association of differentially methylated CpG or genomic regions with gastroparetic symptoms, abnormal (delayed or rapid) gastric emptying, intestinal chemosensitivity, presence or absence of autonomic neuropathy, nephropathy, and retinopathy, will be evaluated; age, gender, glycosylated hemoglobin, and duration of DM are potential covariates.

Reduced representation bisulfite sequencing (RRBS) and analysis will be performed. RRBS is base resolution methylation sequencing to assess genome-wide DNA methylation enriched in CpG rich regions in the genome, particularly in the coding and its neighboring regions. We will use Next Gene Sequencing to determine methylation status as outlined by Gu et al ⁵⁸ and Illumina. Briefly, DNA is digested with MspI and the digested DNA is purified. Purified DNA is end repaired and adenylated. DNA is ligated to Illumina adapters using T4 DNA ligase. Ligated DNA is purified and

size selected using Ampure beads. Purified size selected DNA undergoes bisulfite modification and clean-up. Modified DNA is PCR amplified and purified using Ampure beads. This RRBS library DNA will be run on the Illumina HiSeq2000, indexing 4 samples per lane, using a standard operating procedure based on Illumina's protocol.

An additional 7.5 ml of blood will be collected for mRNA-sequencing and miRNA sequencing in 3 Paxgene tubes (2.5 ml each).

